### **9.3 Data Confidentiality**

Regarding the confidentiality of study data, the provisions of Organic Law 3/2018, of December 5, on the Protection of Personal Data and Guarantee of Digital Rights, and the General Data Protection Regulation (EU) 2016/679, will be followed.

#### **9.4 Interference with the Physician's Prescribing Habits**

The study will not interfere with the clinical management habits of patients.

### **10. PLANS FOR RESULT DISSEMINATION**

It is anticipated that, starting in the second year of the project, the results generated will be presented at leading national and international conferences in diabetes research, such as the Spanish Diabetes Society Conference and the European Diabetes Society Conference.

In addition, a scientific article for each study objective will be published in high-impact journals in the field.

### **11. STUDY RESOURCES**

This project uses the resources and infrastructure of the two participating centers.

At the HSCSP, the Pediatric Endocrinology Unit has three pediatric endocrinology specialists and a nurse specializing in nutrition who is responsible for the diabetes education of patients with T1D. The hospital serves five districts in the city of Barcelona, with a population of over 400,000. It is estimated that the number of new T1D diagnoses is 15 patients per year, to which will be added those diagnosed up to the age of 20. The estimated total is 24 patients. Patients are admitted through the emergency department or referred from other primary care centers and are admitted for one week, at which point the professionals begin nutritional education. The Endocrinology Department at Sant Pau Hospital has a research unit with statistical support available for data evaluation and management, as well as for processing results for analysis.

The Pediatric Endocrinology Unit of the Pediatric Department at HUAV in Lleida has two pediatric specialists with extensive experience in diabetes treatment and a dedicated diabetes educator nurse with specific training in diabetes and nutrition education and years of experience caring for patients. The unit serves a population corresponding to the province of Lleida, as well as patients referred from the Franja de Aragón region. Approximately 15 patients are admitted each year for onset diabetes. Admission care is provided for children up to the age of 15, and newly diagnosed children up to the age of 20 will be added; for an estimated total of 25 patients at this center. Patients receive education upon diagnosis, both from doctors and from nursing professionals, as well as from the diabetes educator. Patients are usually admitted for a week. Subsequently, they are followed up in outpatient clinics by various team professionals. Basic supervision is also provided by the mental health team at the CSMIJ in Lleida. Initial training includes nutritional education, which recommends the ideal number of servings for each patient and their distribution throughout the day, in addition to comprehensive education on healthy dietary habits. It is conducted annually.

Within the teaching function, a course is offered to teaching staff from schools and high schools in the area, in collaboration with the hospital's teaching classroom.

The Sant Joan de Déu Hospital, a leading pediatric hospital in the Barcelona area, is also participating in the study. Its endocrinology unit receives 13,000 visits per year, with consultations for DM1 being one of the most frequent. They have a team of pediatric endocrinologists and nurses who provide educational interventions to

patients and their families during the stay following a DM1 diagnosis. The hospital has a web portal with information, advice, and other resources for patients with DM1 and their families. The number of new DM1 diagnoses varies widely, but the expected recruitment rate is expected with the participation of both hospitals.

These hospitals have affiliated research institutes, the Lleida Biomedical Research Institute, the IR Sant Pau, and the Sant Joan de Déu Research Institute, which have the infrastructure and personnel necessary to carry out the project. The principal investigator of the project belongs to the Sant Pau Research Institute. The crucial leadership of women in this research not only promotes diversity and equity in scientific research but also represents an essential contribution to elevating excellence in biomedical research, opening new paths and approaches in the field of health. [name] is a dietitian-nutritionist, with a PhD in Biomedicine, with extensive experience in the field of basic and translational research focused on nutrition, endocrinology, and complications associated with diabetes. She is an affiliated researcher with the CIBERDEM research group at the Sant Pau Biomedical Research Institute and is part of the Endocrinology, Diabetes, and Nutrition research group, both led by [name]. This group has extensive experience in the study of diabetes and complications associated with dietary and lifestyle habits, which has resulted in a large number of national and international projects and, consequently, scientific publications in high-impact international journals.

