### 4.3 Secondary objectives:

\*Due to the timeliness of the study, we also proposed:

- To characterize changes in the dietary patterns of parents or guardians of patients with T1D during follow-up (6 months after diagnosis).
- To determine, using a questionnaire, changes in the physical activity of the adult subjects in the study at 6 and 12 months.
- To determine, using a questionnaire, the emotional stress produced by the diagnosis and treatment of T1D in the adult parents or guardians belonging to the families of the incident case at 6 and 12 months.
- To determine, using a questionnaire, the level of anxiety and depression produced by the diagnosis and treatment of T1D in the adults in the families at 6 and 12 months.

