#### *5.6.1 Pre-screening*

Each study subject will be identified by the local investigator at each center during the admission of the newly diagnosed patient. Family members (parents or guardians) of all newly diagnosed subjects with a clinical diagnosis of T1D will be invited to participate. Study procedures will be performed by the local investigators at each participating center, who in some cases will be the same pediatric physicians and nurses as the participants' family members with T1D. A dedicated visit will be scheduled with the local investigator at each center to perform all study procedures in a single visit.

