#### *5.6.2 Inclusion*

Each participant invited to participate will be informed about the study both verbally and in writing, using language adapted to their understanding. Participants will be provided with a document called the "Patient Information Sheet" containing all the information of the study, adapted to a simple comprehensive level. No participant will be included until they have been duly informed by the researcher and have freely given their informed consent to participate in the study. Once compliance with all selection criteria has been confirmed and informed consent has been given, data collection will begin by completing an electronic data collection form (EDC), which will record the information available in the patient's medical history or obtained during the inclusion visit.

The inclusion visit will take place within the first week after a family member's T1D diagnosis. This will prevent any lifestyle and dietary changes from being made to the family environment.

The initial clinical evaluation of all included subjects will be performed during the study inclusion visit. Clinical and sociodemographic variables related to the participant (will be collected using an ad-hoc questionnaire and a physical examination. The variables to be collected are defined in **Table 1**. Diet and intake patterns will be collected using questionnaires related to lifestyle and dietary patterns.

These variables will be collected at the inclusion visit, the 6-month follow-up, and at the end of the study at 12 months.

**Table 1.** Study variables

| Variable                            | Source        | Value  |
|-------------------------------------|---------------|--|
| Sociodemographic variables   |               |  |
| Date of birth                       | Questionnaire | dd/mm/yyyy   |
| Age                                 | Questionnaire | Years  |
| Sex                                 | Questionnaire | Male / Female / Other / N/A                                    |
| Gender identity                     | Questionnaire | Male / Female / Other / N/A                                    |
| Area                                | Questionnaire | —  |
| Parents' education level            | Questionnaire | No education / Secondary / Vocational training / University    |
| Family variables             |               |  |
| Number of people in the household   | Questionnaire | Number   |

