## **8. WORK PLAN (tasks, milestones, and study timeline)**

This project is divided into phases:

*Phase 1 (April 2024 - April 2026): Recruitment.*

Recruitment will begin in February, the expected date for obtaining the IRB documentation from each center. This period will last two years.

*Phase 2 (April 2024 - April 2026): First visit.*

Once the participants have been recruited and have signed the IRB, their first visit will include completing the questionnaires, interview, and physical examination. This first visit will take place no more than one week after the child's T1D diagnosis.

*Phase 3 (September 2024 - September 2026): Follow-up.*

The follow-up visit will take place 6 months after the first visit. The questionnaires, interview, and physical examination will be repeated.

*Phase 4 (April 2025 - April 2027): Final visit.*

The final visit will be conducted 12 months after the first visit. The questionnaires, interview, and physical examination will be repeated.

*Phase 5 (September 2026 - April 2027): Data analysis.*

In the final part of the study, the data of the patients who completed the final visit will be analyzed. This will begin with database cleaning and management, analysis, and subsequent interpretation and discussion of the results.

*Phase 6 (April 2027): Study closure.*

Once all final visits are completed, data analysis will be finalized, and communications and manuscripts will be prepared. A research meeting will be held to prepare the final report and close the study.

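### The baseline IPAQ falls in the week of diagnosis and admission with no stated reference period, so later activity change may partly reflect a return to routine

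*Protocol*

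**What the plan says.** **Timing.** Section 5.6.2: "The inclusion visit will take place within the first week after a family member's T1D diagnosis". Section 8, Phase 2, repeats the limit and places the questionnaires at that visit: "This first visit will take place no more than one week after the child's T1D diagnosis". Table 2 schedules the IPAQ at baseline, 6 months and 12 months.

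**Setting.** Under Section 5.6.1, participants are "identified by the local investigator at each center during the admission of the newly diagnosed patient". Section 11 says that HSCSP patients "are admitted for one week, at which point the professionals begin nutritional education". For HUAV it says: "Patients are usually admitted for a week". For Sant Joan de Déu it mentions education given to "patients and their families during the stay following a DM1 diagnosis", with no length of stay.

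**Rationale.** Section 5.6.2 justifies the timing: "This will prevent any lifestyle and dietary changes from being made to the family environment".

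**Instrument.** Section 5.7.1 gives the FFQ a past-year reference period. For the IPAQ it gives only the classification rules, including a sedentary/active split at 30 minutes of moderate activity per day. It names no version and no recall period.

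**Use.** A secondary objective in Section 4.3 is to determine "changes in the physical activity of the adult subjects in the study at 6 and 12 months". Lifestyle change at one year is also part of the primary objective in Section 4.2. Section 6.3 analyses change within person and describes no comparison group. The limitations in Section 6.5 do not mention the admission.

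**The concern.** A pre-post study needs a baseline that represents ordinary life. Here the activity baseline is taken around a child's hospital admission, while both follow-up values come from life at home. The timing rule keeps lasting changes out of the baseline, but it does nothing about the disruption of the admission itself. The FFQ is largely shielded by its past-year recall. The protocol gives the IPAQ no such shield.

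If the recall does cover the admission, part of the measured change is a recovery to normal, and some participants could move from sedentary to active without any lasting change. An apparent increase would agree with the hypothesis in Section 4.1 of an impact on lifestyle, so it could be reported as an effect of education. A statistical analysis plan cannot repair this, because the recall period is fixed when the form is filled in.

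**Working it through.** The protocol gives no figure for physical activity, so there is none to reproduce. Its sample size of 26 family units rests on aMED and is not disputed here.

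**Step 1: does the baseline fall in the admission?** The visit is at most 7 days after diagnosis (Sections 5.6.2 and 8). The stay is one week at HSCSP and usually a week at HUAV (Section 11). At these two centres the baseline IPAQ is therefore normally completed during the stay or right at its end. At Sant Joan de Déu the stay has no stated length, so this cannot be said.

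**Step 2: size of a possible artefact.** These inputs are assumptions, not protocol figures:
- the IPAQ asks about the last 7 days;
- the child is admitted on the day of diagnosis, so a visit on day *d* has *d* of the 7 recalled days in the admission;
- parental activity on those days is a fraction *f* of usual;
- true usual activity does not change, and follow-up measures it correctly.

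Then

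baseline / usual = 1 − (d/7)(1 − f)

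spurious change = 1 / [1 − (d/7)(1 − f)] − 1

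For f = 0.5:
- day 2: 1 − (2/7)(0.5) = 0.857, and 1/0.857 − 1 = 17%
- day 4: 1 − (4/7)(0.5) = 0.714, and 1/0.714 − 1 = 40%
- day 7: 1 − (7/7)(0.5) = 0.500, and 1/0.500 − 1 = 100%

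The range over f:

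| Activity on hospital days (f) | Day 2 | Day 4 | Day 7 |
|---|---|---|---|
| 1.25 (higher than usual) | −7% | −13% | −20% |
| 1.00 (no change) | 0% | 0% | 0% |
| 0.75 | +8% | +17% | +33% |
| 0.50 | +17% | +40% | +100% |
| 0.25 | +27% | +75% | +300% |

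With a usual-week form the recalled admission days drop out and every cell is about 0%. The day-7 column is the extreme case, in which every recalled day is a hospital day.

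**Step 3: could it reach significance?** Take 26 complete pairs, a two-sided paired t-test at 5% and no true change. Let the artefact be *s* standard deviations of the paired difference. The noncentrality is s√26, and the chance of a significant increase is:
- s = 0.2: noncentrality 1.02, about 16%
- s = 0.4: noncentrality 2.04, about 50%
- s = 0.57: noncentrality 2.91, about 80%

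The protocol gives no standard deviation for IPAQ change, so the percentages in Step 2 cannot be converted to *s*. Step 3 shows only that a moderate artefact would be enough.

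**The case against.** The strongest reply is that the two premises behind any bias are not in the protocol. It does not say that the IPAQ recall covers the admission days, and a usual-week form would remove most of the problem. Nor does it say that parents are less active that week. The child is admitted, not the participant. Participants must be responsible for the household's food (Section 5.5.1), and a unit may include both parents (Section 6.4), so some may be at home or share the stay. The visit may fall on any day of the week, and the share of participants from Sant Joan de Déu is unknown. All of this stands, and it limits what can be claimed.

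A reader might infer that baseline activity is biased downward and that an increase will follow. The documents do not support that: the sign depends on *f* and the size on *f*, *d* and the recall window, none of which is given. A reader might also extend the point to the Table 1 item on meals eaten at home. That does not hold. The item sits among descriptors of the household, no stated objective tests it, and nothing says it is answered for the admission week.

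The reply does not remove the gap. The protocol places an activity baseline in an unusual week, leaves its reference period open, and states that the timing guards against lifestyle change.

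**Conclusion.** The point holds in conditional form. The documents establish the timing of the baseline IPAQ, its overlap with the admission at HSCSP and usually at HUAV, the missing reference period, and the lack of a described comparison group. If the recall covers the admission and activity is atypical then, the 0-6 and 0-12 month activity changes mix a return to routine with any lasting change, and the design cannot separate them.

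An increase is the more plausible direction, but it is not shown. On the assumptions of a 7-day window and half-usual activity, the artefact is 17% to 100% depending on the visit day. It is about 0% with a usual-week form or if activity does not fall, and negative if activity rises. The point concerns physical activity, a secondary objective that also feeds the lifestyle part of the primary one. It does not touch the aMED sample size. The change is worth making because it is cheap and no later analysis can recover a pre-admission baseline.

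**What to change.** In Section 5.7.1, state the IPAQ version and its reference period. Anchor the baseline IPAQ to a usual week before the diagnosis and admission, and use the same usual-week wording at 6 and 12 months.

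For participants already enrolled on a form whose recall covers the admission, keep the 0-6 and 0-12 month changes as planned, since change from diagnosis is the objective. Add the 6-12 month change as a supporting analysis, and list the issue in Section 6.5. If the form in use already asks about a usual week before the admission, stating so is enough.

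The cost is a changed instruction on an existing form, with no extra visit or staff. The downside is a slightly longer recall at baseline and a possible departure from the validated wording.

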## **12. PROTOCOL MODIFICATIONS:**

Any modification to the study protocol will always take the form of a written amendment or addendum. Formalization requires the approval of all persons responsible for the study. For significant modifications, express approval from the Clinical Research Ethics Committee will be requested.

## 14. Supplementary material

Semi-quantitative food frequency questionnaire (Translated from the Spanish version)

|   | Never or almost never | Month     | Times/week |     |     | Times/day |     |     |    |
|---|-----------------------|-----------|------------|-----|-----|-----------|-----|-----|----|
|   |                       | 1-3 times | Once       | 2-4 | 5/6 | Once      | 2/3 | 4/6 | +6 |
| Section I: Fruits & Fruit Juices (Items 1–12)                  |                       |           |            |     |     |           |     |     |    |
| 1. Orange (1), grapefruit (1) or tangerines (2)                           |                       |           |            |     |     |           |     |     |    |
| 2. Banana (1)   |                       |           |            |     |     |           |     |     |    |
| 3. Apple or pear (1)  |                       |           |            |     |     |           |     |     |    |
| 4. Fresh orange juice (1 glass, 200 mL)                                   |                       |           |            |     |     |           |     |     |    |
| 5. Bottled or canned fruit juice (200 mL)                                 |                       |           |            |     |     |           |     |     |    |
| 6. Cherries, sour cherries, plums (dessert plate)                         |                       |           |            |     |     |           |     |     |    |
| 7. Grapes (1 bunch or 20 berries)   |                       |           |            |     |     |           |     |     |    |
| 8. Strawberries, raspberries, blackberries (dessert plate)                |                       |           |            |     |     |           |     |     |    |
| 9. Dried fruit (apricots, figs, raisins) (30 g)                           |                       |           |            |     |     |           |     |     |    |
| 10. Other fresh fruit (1 piece or 150 g)                                  |                       |           |            |     |     |           |     |     |    |
| 11. Citrus fruits other than orange or tangerine                          |                       |           |            |     |     |           |     |     |    |
| 12. Fruit salads or compotes (1 bowl)                                     |                       |           |            |     |     |           |     |     |    |
| Section II: Vegetables & Legumes (Items 13–28)                 |                       |           |            |     |     |           |     |     |    |
| 13. Raw leafy greens or salad vegetables (1 plate)                        |                       |           |            |     |     |           |     |     |    |
| 14. Cooked leafy greens (spinach, chard) (1 plate)                        |                       |           |            |     |     |           |     |     |    |
| 15. Raw cruciferous vegetables (broccoli, cauliflower, cabbage) (1 plate) |                       |           |            |     |     |           |     |     |    |
| 16. Cooked cruciferous vegetables (1 plate)                               |                       |           |            |     |     |           |     |     |    |
| 17. Tomatoes (raw or cooked) (1 medium fruit or 1 plate)                  |                       |           |            |     |     |           |     |     |    |
| 18. Bell peppers, cucumber, celery (1 plate)                              |                       |           |            |     |     |           |     |     |    |
| 19. Onion, garlic, leeks (added in cooking) (1 serving)                   |                       |           |            |     |     |           |     |     |    |
| 20. Other cooked vegetables (eggplant, zucchini, carrots) (1 plate)       |                       |           |            |     |     |           |     |     |    |
| 21. Legumes (lentils, chickpeas, beans) (150 g)                           |                       |           |            |     |     |           |     |     |    |
| 22. Peas (150 g)  |                       |           |            |     |     |           |     |     |    |
| 23. Broad beans (150 g)   |                       |           |            |     |     |           |     |     |    |
| 24. Soy products (tofu, edamame) (100 g)                                  |                       |           |            |     |     |           |     |     |    |
| 25. Potatoes (boiled, baked) (1 medium)                                   |                       |           |            |     |     |           |     |     |    |
| 26. French fries or potato chips (1 portion)                              |                       |           |            |     |     |           |     |     |    |
| 27. Pickled vegetables (1 serving)  |                       |           |            |     |     |           |     |     |    |
| 28. Sofrito (tomato/garlic/onion sautéed in olive oil) (1 serving)        |                       |           |            |     |     |           |     |     |    |
| Section III: Cereals & Bread (Items 29–36)                     |                       |           |            |     |     |           |     |     |    |

|  |  |  |  |  |  |  |  |  |
|--|--|--|--|--|--|--|--|--|
| 29. Whole-grain bread (1 slice)                                    |  |  |  |  |  |  |  |  |
| 30. Refined-grain bread (1 slice)                                  |  |  |  |  |  |  |  |  |
| 31. Whole-grain rice, pasta, couscous (1 cup cooked)               |  |  |  |  |  |  |  |  |
| 32. Refined-grain rice, pasta, couscous (1 cup cooked)             |  |  |  |  |  |  |  |  |
| 33. Breakfast cereals (high-fiber) (30 g)                          |  |  |  |  |  |  |  |  |
| 34. Sweetened breakfast cereals (30 g)                             |  |  |  |  |  |  |  |  |
| 35. Oats or muesli (30 g)  |  |  |  |  |  |  |  |  |
| 36. Other grains (quinoa, wheat berries) (1 cup cooked)            |  |  |  |  |  |  |  |  |
| Section IV: Dairy (Items 37–43)                             |  |  |  |  |  |  |  |  |
| 37. Whole-milk yogurt or rice pudding (125 g)                      |  |  |  |  |  |  |  |  |
| 38. Skim- or semi-skimmed-milk yogurt (125 g)                      |  |  |  |  |  |  |  |  |
| 39. Whole-milk (1 glass, 200 mL)                                   |  |  |  |  |  |  |  |  |
| 40. Skim- or semi-skimmed-milk (1 glass, 200 mL)                   |  |  |  |  |  |  |  |  |
| 41. Cheese — hard/semi-hard (30 g)                                 |  |  |  |  |  |  |  |  |
| 42. Fresh cheese (cottage, ricotta) (30 g)                         |  |  |  |  |  |  |  |  |
| 43. Fermented milk drinks (kefir, ayran) (200 mL)                  |  |  |  |  |  |  |  |  |
| Section V: Meats & Eggs (Items 44–58)                   |  |  |  |  |  |  |  |  |
| 44. White meat (chicken, turkey, rabbit) — 1 portion (100–125 g)   |  |  |  |  |  |  |  |  |
| 45. Red meat (beef, pork, lamb) — 1 portion (100–125 g)            |  |  |  |  |  |  |  |  |
| 46. Liver or other organ meats — 1 portion (100–125 g)             |  |  |  |  |  |  |  |  |
| 47. Hamburgers (beef, pork, chicken) — 1 unit                      |  |  |  |  |  |  |  |  |
| 48. Sausages (chorizo, salami, etc.) — 1 portion (50 g)            |  |  |  |  |  |  |  |  |
| 49. Bacon, pancetta — 1 slice                                      |  |  |  |  |  |  |  |  |
| 50. Cold cuts (ham, turkey breast, mortadella) — 1 slice           |  |  |  |  |  |  |  |  |
| 51. Canned meat (corned beef, luncheon meat) — 1 portion (50–75 g) |  |  |  |  |  |  |  |  |
| 52. Meatballs — 1 unit   |  |  |  |  |  |  |  |  |
| 53. Cooked meat (e.g., stews) — 1 portion                          |  |  |  |  |  |  |  |  |
| 54. Breaded or fried meat — 1 portion (100–125 g)                  |  |  |  |  |  |  |  |  |
| 55. Eggs — 1 unit  |  |  |  |  |  |  |  |  |
| 56. Omelet — 1 portion   |  |  |  |  |  |  |  |  |
| 57. Scrambled eggs or eggs with vegetables — 1 portion             |  |  |  |  |  |  |  |  |
| 58. Boiled or fried egg — 1 unit                                   |  |  |  |  |  |  |  |  |
| Section VI: Fish & Seafood (Items 59–67)                |  |  |  |  |  |  |  |  |
| 59. White fish (hake, cod, etc.) — 1 portion (100–150 g)           |  |  |  |  |  |  |  |  |

|   |  |  |  |  |  |  |  |
|---|--|--|--|--|--|--|--|
| 60. Oily fish (salmon, sardines, mackerel) — 1 portion (100–150 g)    |  |  |  |  |  |  |  |
| 61. Salted or smoked fish (cod, salmon, anchovies) — 1 portion (50 g) |  |  |  |  |  |  |  |
| 62. Shellfish (mussels, shrimp, clams) — 1 portion (4–5 units)        |  |  |  |  |  |  |  |
| 63. Canned tuna — 1 small can (80–100 g)                              |  |  |  |  |  |  |  |
| 64. Canned sardines or mackerel — 1 small can (80–100 g)              |  |  |  |  |  |  |  |
| 65. Fish sticks or breaded fish — 1 unit                              |  |  |  |  |  |  |  |
| 66. Fish soup or stew — 1 portion                                     |  |  |  |  |  |  |  |
| 67. Surimi or imitation crab — 1 stick (25 g)                         |  |  |  |  |  |  |  |
| Section VII: Oils, Fats & Sauces (Items 68–77)             |  |  |  |  |  |  |  |
| 68. Extra virgin olive oil — 1 tablespoon (10 mL)                     |  |  |  |  |  |  |  |
| 69. Olive oil (not extra virgin) — 1 tablespoon                       |  |  |  |  |  |  |  |
| 70. Sunflower, corn or soybean oil — 1 tablespoon                     |  |  |  |  |  |  |  |
| 71. Butter — 1 portion (12 g)   |  |  |  |  |  |  |  |
| 72. Margarine — 1 portion (12 g)                                      |  |  |  |  |  |  |  |
| 73. Mayonnaise — 1 tablespoon   |  |  |  |  |  |  |  |
| 74. Cream (liquid or whipped) — 1 tablespoon                          |  |  |  |  |  |  |  |
| 75. Other sauces (ketchup, mustard, barbecue) — 1 tablespoon          |  |  |  |  |  |  |  |
| 76. Pesto, aioli or other oil-based sauces — 1 tablespoon             |  |  |  |  |  |  |  |
| 77. Lard or animal fat — 1 tablespoon                                 |  |  |  |  |  |  |  |
| Section VIII: Beverages (Items 78–94)                          |  |  |  |  |  |  |  |
| 78. Coffee — 1 cup  |  |  |  |  |  |  |  |
| 79. Decaffeinated coffee — 1 cup                                      |  |  |  |  |  |  |  |
| 80. Tea (green, black, etc.) — 1 cup                                  |  |  |  |  |  |  |  |
| 81. Herbal teas (chamomile, mint, etc.) — 1 cup                       |  |  |  |  |  |  |  |
| 82. Milkshakes or flavored milk drinks — 1 glass (200 mL)             |  |  |  |  |  |  |  |
| 83. Soft drinks with sugar — 1 can (330 mL)                           |  |  |  |  |  |  |  |
| 84. Soft drinks without sugar (diet/light) — 1 can (330 mL)           |  |  |  |  |  |  |  |
| 85. Bottled fruit juice (not freshly squeezed) — 1 glass (200 mL)     |  |  |  |  |  |  |  |
| 86. Alcohol-free beer — 1 can/bottle (330 mL)                         |  |  |  |  |  |  |  |
| 87. Beer — 1 can/bottle (330 mL)                                      |  |  |  |  |  |  |  |
| 88. Red wine (young) — 100 mL glass                                   |  |  |  |  |  |  |  |
| 89. Red wine (aged/reserve) — 50 mL glass                             |  |  |  |  |  |  |  |
| 90. White or rosé wine — 100 mL glass                                 |  |  |  |  |  |  |  |
| 91. Cava or sparkling wine — 100 mL glass                             |  |  |  |  |  |  |  |
| 92. Liquor (e.g., whiskey, gin, rum) — 30 mL shot                     |  |  |  |  |  |  |  |

|  |  |  |  |  |  |  |  |
|--|--|--|--|--|--|--|--|
| 93. Sweet liqueurs (Baileys, anise, vermouth)
— 30 mL shot      |  |  |  |  |  |  |  |
| 94. Mixed alcoholic drinks (cocktails, gin & tonic) — 1 glass      |  |  |  |  |  |  |  |
| Section IX: Sweets, Pastries & Snacks (Items 95–113)    |  |  |  |  |  |  |  |
| 95. Pastries (croissants, doughnuts, etc.) — 1 unit                |  |  |  |  |  |  |  |
| 96. Cookies or biscuits — 1 unit or portion (30 g)                 |  |  |  |  |  |  |  |
| 97. Cakes (sponge cake, pie, etc.) — 1 slice                       |  |  |  |  |  |  |  |
| 98. Chocolate (milk or dark) — 1 portion (30 g)                    |  |  |  |  |  |  |  |
| 99. Chocolates with filling or nuts — 1 portion (30 g)             |  |  |  |  |  |  |  |
| 100. Candies, gummies or sweets — 1 portion (30 g)                 |  |  |  |  |  |  |  |
| 101. Honey or jam — 1 tablespoon                                   |  |  |  |  |  |  |  |
| 102. Ice cream — 1 scoop or small cup                              |  |  |  |  |  |  |  |
| 103. Puddings or custards — 1 portion                              |  |  |  |  |  |  |  |
| 104. Snack bars or energy bars — 1 unit                            |  |  |  |  |  |  |  |
| 105. Potato chips — 1 small bag (30 g)                             |  |  |  |  |  |  |  |
| 106. Salted nuts — 1 handful (30 g)                                |  |  |  |  |  |  |  |
| 107. Popcorn (ready-to-eat) — 1 portion (30 g)                     |  |  |  |  |  |  |  |
| 108. Crackers or breadsticks — 1 portion (30 g)                    |  |  |  |  |  |  |  |
| 109. Savory snacks (nachos, cheese balls, etc.) — 1 portion (30 g) |  |  |  |  |  |  |  |
| 110. Sugar cubes or teaspoons added to drinks — 1 unit             |  |  |  |  |  |  |  |
| 111. Artificial sweeteners — 1 packet or dose                      |  |  |  |  |  |  |  |
| 112. Desserts made at home (custards, rice pudding) — 1 portion    |  |  |  |  |  |  |  |
| 113. Diet or sugar-free sweets — 1 portion                         |  |  |  |  |  |  |  |
| Section X: Miscellaneous (Items 114–137)                    |  |  |  |  |  |  |  |
| 114. Pizza (homemade or commercial) — 1 slice or small unit        |  |  |  |  |  |  |  |
| 115. Lasagna or cannelloni — 1 portion                             |  |  |  |  |  |  |  |
| 116. Stuffed pasta (ravioli, tortellini) — 1 portion               |  |  |  |  |  |  |  |
| 117. Prepared foods (frozen meals, ready dishes) — 1 portion       |  |  |  |  |  |  |  |
| 118. Fried rice or noodles — 1 portion                             |  |  |  |  |  |  |  |
| 119. Couscous or bulgur — 1 portion                                |  |  |  |  |  |  |  |
| 120. Vegetable soup — 1 bowl                                       |  |  |  |  |  |  |  |
| 121. Meat or chicken broth — 1 bowl                                |  |  |  |  |  |  |  |
| 122. Fish soup — 1 bowl  |  |  |  |  |  |  |  |
| 123. Mixed salads with dressing — 1 bowl                           |  |  |  |  |  |  |  |
| 124. Mixed dishes (paella, fideuá) — 1 portion                     |  |  |  |  |  |  |  |
| 125. Tapas or appetizers (small bites) — 1                         |  |  |  |  |  |  |  |

|  |  |  |  |  |  |  |  |
|--|--|--|--|--|--|--|--|
| portion  |  |  |  |  |  |  |  |
| 126. Food eaten outside home (per week)                |  |  |  |  |  |  |  |
| 127. Takeaway or fast food (per week)                  |  |  |  |  |  |  |  |
| 128. Vitamin supplements — 1 tablet or dose            |  |  |  |  |  |  |  |
| 129. Mineral supplements — 1 tablet or dose            |  |  |  |  |  |  |  |
| 130. Fiber supplements — 1 dose                        |  |  |  |  |  |  |  |
| 131. Protein powder or shakes — 1 dose                 |  |  |  |  |  |  |  |
| 132. Herbal or natural remedies — 1 dose               |  |  |  |  |  |  |  |
| 133. Meal replacement drinks — 1 bottle (200–250 mL)   |  |  |  |  |  |  |  |
| 134. Sports drinks (isotonic) — 1 bottle (500 mL)      |  |  |  |  |  |  |  |
| 135. Energy drinks (Red Bull, Monster, etc.) — 1 can   |  |  |  |  |  |  |  |
| 136. Artificial supplements or ergogenic aids — 1 dose |  |  |  |  |  |  |  |
| 137. Other food supplements not listed — 1 dose        |  |  |  |  |  |  |  |
